3.2 Derived Data

Prior and Concomitant Medication/Procedure

A prior medication/procedure is any medication/procedure that started prior to date of randomization. A concomitant medication/procedure is any medication/procedure that either has a start date on or after date of randomization, or is ongoing on the date of randomization.

Confidential Document

Hospitalization Status

If a subject experiences multiple hospitalization status types on the given day, the worst status will be summarized on the day of interest.

NEWS2 Score

Chart 1: The NEWS2 scoring system

Physiological parameter	Score						
	3	2	1	0	1	2	3
Respiration rate (per minute)	≤8		9–11	12–20		21–24	≥25
SpO ₂ Scale 1 (%)	≤91	92–93	94–95	≥96			
SpO ₂ Scale 2 (%)	≤83	84–85	86–87	88–92 ≥93 on air	93–94 on oxygen	95–96 on oxygen	≥97 on oxygen
Air or oxygen?		Oxygen		Air			
Systolic blood pressure (mmHg)	≤90	91–100	101–110	111–219			≥220
Pulse (per minute)	≤40		41–50	51–90	91–110	111–130	≥131
Consciousness				Alert			CVPU
Temperature (°C)	≤35.0		35.1–36.0	36.1–38.0	38.1–39.0	≥39.1	

Use Chart 1 NEWS2 scoring system to derive NEWS2 score of each physiological parameter collected from case report forms. If hypercapnic respiratory failure, use SpO₂ Scale 2; otherwise use SpO₂ Scale 1. The total possible score ranges from 0 to 20. If any one of the NEWS2 parameters is not available on the study visit, the NEWS2 score will not be derived.

Confidential Document

	CCB-CRISIS-01 Statistical Analysis Plan	Revision No. 1.0
	Document Date: 17-Dec-2020	Page 13 of 17

Normalization

In order to summarize inflammatory marker results across the laboratories which have different normal ranges, normalization will be performed. The scale model will be applied for data transformation using the scale normalization formula:

$$S = X \times \frac{ULN_s}{ULN_x}$$

where X represents an assay value from the local laboratory, ULN_x is the ULN from the laboratory, and ULN_s is the upper limit of normal (ULN) from Site 02. Markers that are performed only at the central laboratory will not be normalized.

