2.5.3 Exploratory Efficacy Analyses

Changes from baseline will be summarized by treatment:

- Viral load (nasopharyngeal) (Days 3, 5, 7, and 15)
- Inflammatory markers (Days 3, 5, 7, and 15)
- DHO levels (Days 3, 5, 7, and 15)
- Brequinar concentration levels (Days 3, 5 and 7)

For inflammatory markers (including pro-inflammatory cytokines), results from both local and central laboratories will be combined, where the local test result will be normalized where necessary. (See [Section 3.2](#) for normalization method).

Viral culture results will be provided in data listings only.

Confidential Document

	CCB-CRISIS-01 Statistical Analysis Plan	Revision No. 1.0
	Document Date: 17-Dec-2020	Page 10 of 17

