3. DATA HANDLING

3.1 Baseline and Study Visits

Study Day 1 will be the day of randomization.

The summary of hospitalization status will be based on the Study Day (derived relative to the day of randomization).

For the summary of inflammatory markers, Baseline will be the last assessment prior to dosing (SOC plus brequinar group) or last assessment on or prior to Study Day 1 (SOC group). Post-baseline timepoints will be based on the Study Day (derived relative to the day of randomization), where Day 15 includes a 4-day window (Study Day 11-19). If there are multiple results on the same day, the earliest result will be used.

For all other summaries, post-baseline timepoints will use the visit as recorded on the case report form, and Baseline will be the last non-missing value prior to randomization, including unscheduled assessments. Otherwise, unscheduled data will not be used in the analyses, but will be presented in the listings.

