Summary of Change from Baseline in SARS-CoV-2 Viral Load (copies/mL) by Treatment and Visit
Modified Intent-to-Treat Population

Visit	SOC + Brequinar (N=xx)		SOC (N=xx)	
	Visit	Change from Baseline	Visit	Change from Baseline
Baseline				
n	xx		xx	
Mean (SE)	xx.x (xx.xx)		xx.x (xx.xx)	
Median	xx.x		xx.x	
Q1, Q3	xx.x, xx.x		xx.x, xx.x	
Min, Max	xx, xx		xx, xx	
Day 3				
n	xx	xx	xx	xx
Mean (SE)	xx.x (xx.xx)	xx.x (xx.xx)	xx.x (xx.xx)	xx.x (xx.xx)
Median	xx.x	xx.x	xx.x	xx.x
Q1, Q3	xx.x, xx.x	xx.x, xx.x	xx.x, xx.x	xx.x, xx.x
Min, Max	xx, xx	xx, xx	xx, xx	xx, xx
Day 5				
n	xx	xx	xx	xx
Mean (SE)	xx.x (xx.xx)	xx.x (xx.xx)	xx.x (xx.xx)	xx.x (xx.xx)
Median	xx.x	xx.x	xx.x	xx.x
Q1, Q3	xx.x, xx.x	xx.x, xx.x	xx.x, xx.x	xx.x, xx.x
Min, Max	xx, xx	xx, xx	xx, xx	xx, xx
etc.				
Source: Listing 16.2.x				

Programming note: Include Day 3,5,7,15.

Clear Creek Bio, Inc.: Protocol CCB-CRISIS-01

Table 14.2.6

Summary of Change from Baseline in Inflammatory Markers by Treatment and Visit
 Modified Intent-to-Treat Population

Parameter Visit	SOC + Brequinar (N=xx)		SOC (N=xx)	
	Visit	Change from Baseline	Visit	Change from Baseline
Parameter 1 (unit), Normal Range=xx-xx Baseline				
n	xx		xx	
Mean (SE)	xx.x (xx.xx)		xx.x (xx.xx)	
Median	xx.x		xx.x	
Q1, Q3	xx.x, xx.x		xx.x, xx.x	
Min, Max	xx, xx		xx, xx	
Day 3				
n	xx	xx	xx	xx
Mean (SE)	xx.x (xx.xx)	xx.x (xx.xx)	xx.x (xx.xx)	xx.x (xx.xx)
Median	xx.x	xx.x	xx.x	xx.x
Q1, Q3	xx.x, xx.x	xx.x, xx.x	xx.x, xx.x	xx.x, xx.x
Min, Max	xx, xx	xx, xx	xx, xx	xx, xx
Day 5				
n	xx	xx	xx	xx
Mean (SE)	xx.x (xx.xx)	xx.x (xx.xx)	xx.x (xx.xx)	xx.x (xx.xx)
Median	xx.x	xx.x	xx.x	xx.x
Q1, Q3	xx.x, xx.x	xx.x, xx.x	xx.x, xx.x	xx.x, xx.x
Min, Max	xx, xx	xx, xx	xx, xx	xx, xx
etc.				
Parameter 2 (unit), Normal Range=xx-xx Baseline				
Source: Listing 16.x.x.x				

Programming note: Include all parameters from local and central labs on Day 3, 5, 7, 15.

Clear Creek Bio., Inc.: Protocol CCB-CRISIS-01

Table 14.2.7

Summary of Change from Baseline in DHO Level (ng/mL) by Treatment and Visit

Intent-to-Treat Population

Visit	SOC + Brequinar (N=xx)		SOC (N=xx)	
	Visit	Change from Baseline	Visit	Change from Baseline
Baseline				
n	xx		xx	
Mean (SE)	xx.x (xx.xx)		xx.x (xx.xx)	
Median	xx.x		xx.x	
Q1, Q3	xx.x, xx.x		xx.x, xx.x	
Min, Max	xx, xx		xx, xx	
Day 3				
n	xx	xx	xx	xx
Mean (SE)	xx.x (xx.xx)	xx.x (xx.xx)	xx.x (xx.xx)	xx.x (xx.xx)
Median	xx.x	xx.x	xx.x	xx.x
Q1, Q3	xx.x, xx.x	xx.x, xx.x	xx.x, xx.x	xx.x, xx.x
Min, Max	xx, xx	xx, xx	xx, xx	xx, xx
Day 5				

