xx-xxxx	Day 1		9999-99-99	99:99	BLOQ (<5)	xxxx
	Day 3		9999-99-99	99:99	xxx	xxxx
	Day 5		9999-99-99	99:99	xxx	xxxx
	Day 7		9999-99-99	99:99	xxx	BLOQ (<5)
	Day 15		9999-99-99	99:99	xxx	xxxx
a: BLOQ = Below Limit of Quantification (limit of quantification in parentheses)						

Clear Creek Bio, Inc.: Protocol CCB-CRISIS-01

Listing 16.2.6.1

Listing of NEWS2 Assessments by Treatment

Site-Subject	Visit	Date and Time Collected	SBP ^a (mmHg)	DBP ^a (mmHg)	Pulse (Beats/Min.)	Respiration (Breath/Min.)	SpO ₂ / SaO ₂ (%)	Temp. (Celsius)	Supplemental Oxygen?	Hypercapnic respiratory failure?	Alert?	NEWS 2 Score
SOC + Brequinar												
xx-xxxx	Day 1	9999-99-99T99:99	xxx	xxx	ND	xxx	xxx	xx.x	Yes	Yes	Yes	xx
	Day 3	9999-99-99T99:99	xxx	xxx	xxx	xxx	xxx	xx.x	Yes	No	No	xx
	Day 5	9999-99-99T99:99	xxx	xxx	xxx	xxx	ND	xx.x	No	Yes	No	xx
	Day 7	Not Done										
	Day 15	9999-99-99T99:99	xxx	xxx	xxx	xxx	xxx	xx.x	No	Unknown	Yes	xx
SOC												
xx-xxxx	Day 1	9999-99-99T99:99	xxx	xxx	xxx	ND	xxx	xx.x	xxx	xxx	xxx	xx
	Day 3	9999-99-99T99:99	xxx	xxx	xxx	xxx	xxx	ND	xxx	xxx	xxx	xx
	Unscheduled											
	Day 5	9999-99-99T99:99	xxx	xxx	xxx	xxx	xxx	xx.x	xxx	xxx	xxx	xx
	Day 7	9999-99-99T99:99	ND	ND	xxx	xxx	xxx	xx.x	xxx	xxx	xxx	xx
	Day 15	9999-99-99T99:99	xxx	xxx	xxx			xx.x	xxx	xxx	xxx	xx
Note: ND=Not Done a: SBP=Systolic Blood Pressure, DBP=Diastolic Blood Pressure.												

Clear Creek Bio, Inc.: Protocol CCB-CRISIS-01

Listing 16.2.6.2

Listing of Inflammatory Markers by Treatment

Parameter	Visit	Not Done	Laboratory	Date and Time Collected	Result	Abnormal?	Reference Range	
SOC + Brequinar								
Site-Subject= xx-xxxx								
Parameter 1 (unit)	Day 1	Not Done	Local	9999-99-99T99:99	xx.x	High		
	Day 3		Local	9999-99-99T99:99	xx.x	High		
	Day 5		Central	9999-99-99T99:99	xx.x			
	Day 7							
	Day 15		Local	9999-99-99T99:99	xx.x			
Parameter 2 (unit)	Day 1	Not Done	Local	9999-99-99T99:99	xx.x	Abnormal		
	Day 3		Local	9999-99-99T99:99	xx.x			
	Unscheduled		Local	9999-99-99T99:99	xx.x			
	Day 5		Local	9999-99-99T99:99	xx.x			
	Day 7							
	Day 15		Local	9999-99-99T99:99	xx.x			
SOC								
Site-Subject= xx-xxxx								
Parameter 1 (unit)	Day 1		Central	9999-99-99T99:99	xx.x			
	Day 3		Central	9999-99-99T99:99	xx.x			
	Day 5		Central	9999-99-99T99:99	xx.x			
	Day 7		Central	9999-99-99T99:99	xx.x			
	Day 15		Central	9999-99-99T99:99	xx.x			

Programming note: Include all data collected in local and central labs, including the tests done in both labs or done multiple times.

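### The SAP scales local inflammatory-marker results to Site 02's ULN but gives no rule putting central results of the same markers on that scale, yet it pools the two

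*SAP*

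**What the plan says.** Four places in the SAP bear on this point.

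- **Section 2.5.3 (exploratory analyses)** states that for inflammatory markers "results from both local and central laboratories will be combined, where the local test result will be normalized where necessary". It does not define when normalization is necessary.
- **Section 3.2 (Normalization)** gives the purpose as summarizing results "across the laboratories which have different normal ranges". The formula is S = X × ULN_s / ULN_x, "where X represents an assay value from the local laboratory", and "ULN_s is the upper limit of normal (ULN) from Site 02". The paragraph closes: "Markers that are performed only at the central laboratory will not be normalized".
- **Section 3.1** fixes which result is used. Baseline is the last assessment before dosing (brequinar arm) or on or before Study Day 1 (SOC arm). For duplicates, "If there are multiple results on the same day, the earliest result will be used". Neither rule refers to the laboratory.
- **The mock tables and listings** show one normal range per parameter in Table 14.2.6, with the note "Include all parameters from local and central labs on Day 3, 5, 7, 15". The note to Listing 16.2.6.2 reads "Include all data collected in local and central labs, including the tests done in both labs or done multiple times".

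**The concern.** Scaling by ULN makes results comparable only if every pooled value ends on the same reference. The SAP names Site 02's ULN as that reference but defines the input as a local value. A marker run only at the central laboratory stays on one scale and raises no problem. A marker run at both has its local values moved to the Site 02 scale, and no sentence moves its central values there.

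A programmer who follows the definition of X would leave those central values raw and enter them in the same means, medians and changes from baseline. A change of laboratory within a subject would then appear as a change in the marker. Subjects measured at different types of laboratory would contribute changes in different units. That defeats the section's stated purpose.

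**Working it through.** The SAP gives no ULN for any marker or laboratory, so there is no figure of its own to reproduce. The check applies the SAP's formula to assumed ULNs.

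**Inputs**

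- Formula, definition of X and target ULN_s: SAP Section 3.2.
- Pooling of sources: Section 2.5.3 and Table 14.2.6.
- Assumed: ULN_02 = 10 units, a true level constant at k = 3 times the ULN, and ULN_central/ULN_02 between 0.5 and 2.

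**Step 1: the scale model.** This model holds that a given true level reads as the same multiple k of the ULN in every laboratory.

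- Scaled local value: (k × ULN_local) × ULN_02 / ULN_local = k × ULN_02 = 3 × 10 = 30.0. The local ULN cancels.
- Raw central value: k × ULN_central.
- Spurious relative change on a local-to-central move: (k × ULN_central) / (k × ULN_02) − 1 = ULN_central/ULN_02 − 1.

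| Assumed ULN_central/ULN_02 | Scaled local | Raw central | Spurious change |
|---|---|---|---|
| 0.5 | 30.0 | 15.0 | −50% |
| 0.8 | 30.0 | 24.0 | −20% |
| 1.0 | 30.0 | 30.0 | 0% |
| 1.25 | 30.0 | 37.5 | +25% |
| 1.5 | 30.0 | 45.0 | +50% |
| 2.0 | 30.0 | 60.0 | +100% |

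**Step 2: no switch within a subject.** The units still differ between subjects. A true fall from 3 to 2 times the ULN is recorded as 20 − 30 = −10 for a subject measured locally throughout. For a subject measured centrally throughout it is 10 − 15 = −5 if ULN_central = 5, and 40 − 60 = −20 if ULN_central = 20.

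**Step 3: the formula applied to central results too.** With ULN_x = ULN_central, the central value becomes (k × ULN_central) × ULN_02 / ULN_central = k × ULN_02 = 30.0. The spurious change is 0 at every ratio in the table. Setting ULN_s to the central ULN does the same, because both sources then equal k × ULN_central.

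**Step 4: sensitivity to the model.** Suppose instead that the assays share one calibration and differ only in the ULN they quote. With a true value T, scaled local is T × ULN_02/ULN_local and raw central is T. The spurious change on a local-to-central move is then ULN_local/ULN_02 − 1, again −50% to +100% for assumed ratios of 0.5 to 2. A common ULN_s does not remove this: with both sources scaled, the change is ULN_local/ULN_central − 1. That is a limit of ULN scaling itself, which the SAP has chosen; it is separate from the gap described here.

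**The case against.** The strongest reply rests on the last sentence of the Normalization paragraph. An exemption for markers run only centrally is needed only if central results could otherwise be normalized, so it may imply that central results of shared markers do pass through the formula. The paragraph's purpose is to bring laboratories with differing ranges together, and ULN_x is described as coming from the laboratory, without the word local. On that reading all shared-marker values reach the Site 02 scale and there is no defect. The reading is possible, but it conflicts with the definition of X as a local value, and Section 2.5.3 names the local result as the one normalized. If it is the intent, the text still needs correcting.

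Other parts of the reply stand, and they limit what a reader may infer:

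- Section 2.5.3 names the local result but does not say that it alone is normalized. It also leaves the condition for normalizing undefined.
- Listing 16.2.6.2 shows one parameter as local, then central, then local again. A reader might take this as evidence that subjects switch laboratories. The rows are placeholders. They and the note show that results from both sources are foreseen, but say nothing about how often.
- A reader might infer that switches could create or hide an anti-inflammatory effect. A systematic difference between arms needs laboratory use that differs by arm. The SAP gives no number of shared markers, no switch rate and no sign of imbalance.
- The same-day rule is prespecified and does not depend on outcome. Once all values share one scale, preferring the laboratory that supplied baseline is optional.
- Listing 16.2.6.2 has columns for laboratory and reference range, so a change of laboratory could be found in the listing, though not in the table.

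**Conclusion.** The concern holds for inflammatory markers measured at both local and central laboratories. For these, the formula is written for local values with Site 02's ULN as target, no rule covers the central values, and both are combined in Table 14.2.6. Followed literally, this pools two scales.

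Under the scale model, a local-to-central move adds ULN_central/ULN_02 − 1 to the relative change, or −50% to +100% over assumed ratios of 0.5 to 2. The size in this trial is unknown because no ULNs are given. It is zero if Site 02's and the central laboratory's limits agree, although the section's premise is that ranges differ. The documents do not support a claim that the arms would be biased, or in which direction.

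The consequence is confined to an exploratory, descriptive summary. Section 3.2 prescribes this normalization for inflammatory markers alone, so the primary safety objective and the safety laboratory tables are untouched. The correction is still worth making: the rule as written can give a wrong change from baseline, and putting it right costs almost nothing.

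**What to change.** 1. In Section 3.2, define X as an assay value from any laboratory, local or central, for every marker run at more than one laboratory. Define ULN_x as the ULN of the laboratory that produced X.
2. Name one common ULN_s for all such values. Site 02's or the central laboratory's will serve, provided it applies to every pooled result and is the range shown in Table 14.2.6.
3. Leave unnormalized only the markers run at the central laboratory alone, as now.
4. In Section 2.5.3, replace the open condition *where necessary* with a reference to this rule.

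A same-day preference for the laboratory that supplied baseline may be added to Section 3.1 but is not required.

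The cost is a few sentences in two sections and a small change to the derivation program. No new data are needed.

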3.3 Missing Data and Data Conventions

No imputation is planned for missing data.

The follow conventions will be used for data handling:

- If SARS-Cov-2 is “not detected” in specimen, the test result will be set to 0 for analysis.
- For DHO and brequinar concentration levels, samples below the lower limit of quantitation (LLOQ) will be set to half of the LLOQ value for the summary tables (LLOQ of DHO is 5 ng/mL, LLOQ of concentration level is 5 mcg/mL).
- If a laboratory test result is reported as “< xxx” or “> xxx”, the value of “xxx” will be used for analysis.
- If a medication or procedure has an incomplete start date, it is assumed to have started prior to randomization, unless the month and year are after randomization.
- If a medication or procedure is not checked as ongoing and has an incomplete stop date, it is assumed to have stopped after randomization, unless the month and year are prior to randomization.

Confidential Document

	CCB-CRISIS-01 Statistical Analysis Plan	Revision No. 1.0
	Document Date: 17-Dec-2020	Page 14 of 17

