1. INTRODUCTION

1.1 Background

Beginning in December 2019, Chinese scientists isolated a novel coronavirus, severe acute respiratory syndrome coronavirus 2 (SARS-CoV-2) from patients with virus-infected pneumonia which was later designated as coronavirus disease 2019 (COVID-19) by the World Health Organization (WHO). Approximately 14% of those affected with this virus will develop severe disease requiring hospitalization and oxygen support; 5% will require admission to the intensive care unit (ICU). Coronaviruses, like other Ribonucleic acid (RNA) based viruses, do not have the machinery to synthesize their own nucleotides and thus depend upon the host intracellular pool of nucleotides for viral replication. In essence, viruses steal the host RNA building blocks, and without these building blocks they are unable to replicate.

Dihydroorotate dehydrogenase (DHODH) is a clear therapeutic target for the inhibition of host pyrimidine synthesis. Brequinar is an orally available and potent inhibitor of DHODH. Brequinar is one of more than 300 quinoline-carboxylic acid derivatives prepared in an analog synthesis program in the 1980s, which was started after it was found that a compound of this class had antitumor activity.

The CRISIS trial will study standard of care (SOC) and SOC with 5 days of DHODH inhibition. Clear Creek Bio hypothesizes that a defined 5-day course of brequinar will inhibit the enzyme DHODH to a degree sufficient to result in the transient depletion of host pyrimidine nucleotides, thereby inhibiting viral replication.

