1.2.1 Number of Subjects and Randomization

Subjects who meet all the inclusion and none of the exclusion criteria will be enrolled in the study until approximately 24 subjects have completed the study. Subjects will be randomized to either SOC or SOC plus brequinar or in a 1:2: ratio (approximately 8 subjects assigned to SOC alone and approximately 16 subjects on SOC plus brequinar).

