1.3.3 Exploratory Objectives

- To determine the change in SARS-CoV-2 nasopharyngeal viral load through Day 15
- To determine the change in inflammatory markers through Day 15
- To determine the change in DHO levels through Day 15
- To determine the change in brequinar concentration levels through Day 7

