2. STATISTICAL METHODOLOGY

2.1 General Principles

In general, continuous parameters will be summarized by number of non-missing observations (N), mean, standard error (SE), median, quartiles, minimum, and maximum. Categorical parameters will be summarized by count and percentage of the non-missing observations, and

Confidential Document

	CCB-CRISIS-01 Statistical Analysis Plan	Revision No. 1.0
	Document Date: 17-Dec-2020	Page 8 of 17

95% confidence interval (CI), when appropriate. All statistical analyses will be performed using SAS® Version 9.4. Adverse events (AEs), procedures and medical history will be coded using Medical Dictionary for Regulatory Activities (MedDRA) Version 23.0. Prior and concomitant medications will be coded using World Health Organization Drug Dictionary (WHODrug) Enhanced March 2020. Common Terminology Criteria for Adverse Events (CTCAE) Version 4.03 will be utilized for adverse event and laboratory reporting.

All study data collected will be presented in listings.

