2.2 Sample Size Determination

Formal sample size calculations are not applicable for this phase 1a, open label study. Up to 24 subjects are planned to be entered in this trial. Additional subjects may be enrolled following data review.

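### Table 14.2.5 summarises viral load change in raw copies/mL with non-detects at 0, so its change columns mostly track baseline titre; log10 copies/mL would serve better

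*SAP*

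**What the plan says.** Viral load is the first exploratory objective in SAP Section 1.3.3: "To determine the change in SARS-CoV-2 nasopharyngeal viral load through Day 15". Section 2.5.3 plans a descriptive summary of change from baseline by treatment at Days 3, 5, 7 and 15. The shell for Table 14.2.5 fixes the scale in its title: "Summary of Change from Baseline in SARS-CoV-2 Viral Load (copies/mL) by Treatment and Visit". It has one column for the visit value and one for the change. Each is described by n and by the statistics that Section 2.1 lists: "mean, standard error (SE), median, quartiles, minimum, and maximum".

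For specimens in which the virus is not detected, Section 3.3 states "in specimen, the test result will be set to 0 for analysis". The next item in that section handles DHO and brequinar concentrations differently: values below the quantification limit become half that limit. No detection or quantification limit is given for the viral load assay. Neither the text nor the shells mention a log10 transformation, a geometric mean or the proportion undetectable. Individual results appear in Listing 16.2.6.3.

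Section 1.2.1 gives the arm sizes: "approximately 8 subjects assigned to SOC alone and approximately 16 subjects on SOC plus brequinar". Section 2.2 states "Formal sample size calculations are not applicable for this phase 1a, open label study", and no test on viral load is planned.

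**The concern.** Viral load usually spans orders of magnitude. On the raw scale an arm's mean is then set by its few highest values, and a subject's change is close to minus the baseline value whatever the treatment did. With arms of about 8 and 16, randomisation cannot be relied on to balance the highest baselines.

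The table matters more than its exploratory label suggests. The hypothesis in Section 1.1 ends with "thereby inhibiting viral replication". Viral culture is listed only (Section 2.5.3), and plasma viral load will not be collected (Section 4). Table 14.2.5 is therefore the only planned tabulated summary of antiviral activity. If its change columns often favour the wrong arm, a reader could take the wrong message from the trial about mechanism.

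**Working it through.** **Inputs.** From the SAP: arms of about 16 and 8, raw copies/mL, non-detects at 0. The SAP states no variance, effect size or power for viral load, so there is no figure of its own to reproduce. Everything else here is assumed: lognormal load with mean 6 log10 copies/mL; between-subject SD 0.5 to 2.0 log10; detection limit 100 copies/mL; a fall of 1 log10 on SOC and 2 log10 on brequinar; SD of the log10 change 0.75, 1.0 or 1.5.

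**1. What raw change measures.** A fall of k log10 gives change = baseline × (10^−k − 1).
- k = 1: −0.9 × baseline
- k = 2: −0.99 × baseline
- k = 3: −0.999 × baseline

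For a common baseline, a 3-log10 fall exceeds a 1-log10 fall by 0.999/0.9 = 1.11, or 11%. A 2-log10 fall exceeds it by 0.99/0.9 = 1.10, or 10%.

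**2. Chance imbalance at baseline.** The standard error of the difference between arms in mean log10 baseline is SD × √(1/16 + 1/8) = SD × 0.433. At SD 1.0 one standard error is a factor of 10^0.433 = 2.7. At SD 2.0 it is 10^0.866 = 7.3. A 10% treatment signal in raw change thus sits beside chance baseline differences of 2.7-fold or more.

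**3. Concentration in the highest subjects.** Median share of an arm's raw baseline total held by its top two subjects (20,000 simulated arms):

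| log10 SD | n = 8 | n = 16 |
|---|---|---|
| 0.5 | 59% | 42% |
| 1.0 | 83% | 71% |
| 1.5 | 93% | 86% |
| 2.0 | 98% | 94% |

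**4. Direction of the comparison between arms.** Share of 20,000 simulated trials in which the statistic favours SOC although brequinar truly has the extra 1-log10 fall. Ranges run over the three SDs of change. The log10 column sets non-detects to half the assumed detection limit.

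| Baseline log10 SD | Raw mean change | Raw median change | Raw visit median | Mean log10 change |
|---|---|---|---|---|
| 1.0 | 29–33% | 32–37% | 5–13% | 0–7% |
| 1.5 | 31–33% | 34–40% | 11–16% | 0–7% |
| 2.0 | 31–33% | 35–42% | 16–19% | 0–8% |

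The median does not rescue the change column. The visit median does much better.

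**5. What the zero does.** For arms of 16 with log10 mean 4 and SD 1.5, coding non-detects as 0 rather than 100 copies/mL moves the raw mean by a median of about 0.001% (95th percentile 0.03%). The zero does not create the dominance in step 3. Its fault is that log10(0) is undefined, so the better scale cannot be used while the convention stands.

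**6. Sensitivity of the log10 analysis to the substituted value.** Using the full limit instead of half moves each non-detect by log10 2 = 0.30. In the simulations the largest gap between arms in the post-baseline share not detected was 10 percentage points (19% v 9%). That moves the difference between arms by about 0.10 × 0.30 = 0.03 log10, against an assumed effect of 1.

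**The case against.** The strongest reply is that the table is not limited to the mean. It also gives medians, quartiles and range, for visit values as well as change, and Listing 16.2.6.3 shows every result. The visit column does not suffer from step 1: falls of 1 and 3 log10 leave 0.1 and 0.001 of baseline, a 100-fold difference. Raw visit medians order the arms correctly in 81–95% of the simulated trials. All of this stands. A reader might infer that the plan makes an antiviral effect impossible to see, and the documents do not support that.

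Three other tempting readings also fail.
- **The zero rule makes a few subjects dominate the mean.** Step 5 shows that the raw scale does this.
- **Zero and the rule for results reported as below a limit put low values on incompatible scales.** Both are in copies/mL and correctly ordered, and the SAP does not show that this assay reports results in that form.
- **The plan lacks power.** As a yardstick, a Welch test at two-sided 0.05 would detect the assumed effect in 1–4% of trials on raw change and 26–81% on log10 change. The SAP plans no such test, so these figures do not describe a planned inference.

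It is also fair that every variance and effect is assumed, that concentration is much weaker at SD 0.5, and that a zero is a code that can be replaced before taking logs. The last point is a reason to change the convention in the SAP now rather than leave it to a later analyst.

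**Conclusion.** The point holds as a weakness in an exploratory, descriptive table. On the raw scale the change columns mostly reflect baseline titre. Under the assumptions above, mean and median raw change favour the wrong arm in roughly 30–40% of trials (29–42% across the settings run), against 0–8% for log10 change. That change is close to minus baseline is plain arithmetic. The percentages rest on a lognormal load with log10 SD 1.0 to 2.0, a 1-log10 extra fall and a detection limit of 100 copies/mL. Direction errors were not simulated at SD 0.5.

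The zero code is a secondary fault: it leaves log10 undefined and departs from the half-limit rule used for DHO and brequinar in the same section. The consequence is a table that is hard to interpret and can mislead. It is not a failed inference, so this is a cheap improvement worth making rather than an essential correction.

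**What to change.** - In Section 3.3, replace the zero rule with text such as: *Viral load will be analysed as log10 copies/mL. Results of not detected will be set to half the assay's detection limit; results detected but below the quantification limit will be set to [stated value between that and the quantification limit].* State both limits, which the SAP does not give at present.
- Retitle Table 14.2.5 as change from baseline in log10 copies/mL, keeping the same statistics.
- Add a row for n (%) not detected at each visit.
- Keep raw copies/mL in Listing 16.2.6.3.
- Optionally, add a baseline-adjusted difference between arms with a 95% confidence interval. The descriptive aim does not require it.

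The cost is a short change to Section 3.3, a retitled shell and one extra row, with no new data. The result will depend slightly on the substituted value (about 0.03 log10 in step 6), and the row for non-detects lets a reader judge that.
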